7.2.3 Withdrawal from Study Criteria

Reasons for discontinuation from the study include, but are not limited to, the following:

- Adverse Event
- Pregnancy
- Withdrawal By Subject
- Lost To Follow-Up. The Investigator will try to reach the subject, twice by telephone (document telephone calls) and once by certified letter, before considering the subject lost-to-follow-up. The lost to follow-up discontinuation will be reported on the appropriate eCRF, and a copy of the follow-up letter will be maintained in the Investigator's file.
- Study Terminated By Sponsor
- Physician Decision
- Non-Compliance with Study
- Other

All premature discontinuations from the study must be documented by the Investigator on the eCRF, and if due to an adverse event, on the Adverse Event Case Report page of the eCRF. All subjects should attempt to complete all visits and evaluations.

Subjects not completing the entire study should be fully evaluated (i.e., final double-blind Week 12 visit procedures performed during the double-blind period or the final open label Week 52 visit procedures during the open-label period). All subjects are free to withdraw from participating in this study at any time and for whatever reason, specified or unspecified, and without prejudice to his or her medical care by a physician. Subjects who withdrawal from the study will not be replaced.

CONFIDENTIAL

Version Date: 31 March 2017

7.3 CONDUCT OF STUDY

7.3.1 Table of Study Procedures

Procedures	Screening (Within 30 days of Baseline)	Double-Blind (DB) Study Period			Open-Label Extension Study Period	
		Baseline/ Day 1 (prior to study drug application)	Interim Visits: Weeks 1, 3, 6 and 9 (± 3 days)	Final DB Visit/ET: Week 12 (± 3 days)	Study Week 16, 26 and 39 (± 14 days)	Final Open-Label Study Visit/ET ⁴ Week 52 (± 14 days)
Informed Consent	X					
Demographics, Medical and Rosacea History	X	X				
Previous Medications	X					
Concomitant Therapy/Medication Review	X	X	X	X	X	X
Limited Physical Exam	X			X		X
Vital Signs	X		X (week 6 only)	X		X
Blood collection for clinical laboratory testing	X			X		X
Blood collection for immunogenicity testing		X	X (week 3 & 6)	X	X (except Week 16)	X
Urine Pregnancy Test, if applicable	X			X		X
Investigators Global Assessment (IGA)	X	X	X	X	X	X
Investigators Assessment of Erythema (IAE)	X	X	X	X		
Other Signs and Symptoms Assessment	X	X	X	X		
Inflammatory Lesion Counts	X	X	X	X	X (week 26)	X
Inclusion/Exclusion Criteria	X	X				
Randomization		X				
Dispense Study Drug		X	X ¹	X Open-label	X	
Dispense Diary		X	X	X Open-label	X	
Drug Accountability / diary review / compliance check, and Collection of Drug and diary			X	X	X	X
Instruct on Treatment Application		X		X Open-label		
Apply Study Drug		X ²	X	X	X	X
Adverse Event Assessment		X ³	X	X	X	X

¹ Study drug will not be dispensed at the Week 1 visit.

² The first application of study drug will be performed at the study center.

³ Adverse event assessment during the Baseline visit will be performed following the first application of study drug.

⁴ The end of the study will be the date that the last study subject completes the last visit for the study.

CONFIDENTIAL

Version Date: 31 March 2017

7.3.2 Study Procedures by Visit

Visits following the Baseline Visit are to occur at the end of Weeks 1, 3, 6, 9, and 12 (Final Double-Blind Visit). However, interim study visits and the Final Week 12 study visit may be conducted (on an individual subject basis) up to 3 days before or after the regularly scheduled study visit. Additional open-label safety extension visits occur at Weeks 16, 26, 39, and the final extension visit at Week 52. An unscheduled visit may occur in the event that the investigator determines that the subject should be seen for safety or any other reasons.

7.3.2.1 Screening Visit

The following procedures will be performed during the Screening visit:

- Obtain subject's written informed consent prior to initiating any study procedures, including instructing the subject to discontinue use of medication that requires a washout (see Section 7.6.11.1). Provide subject with a copy of signed and dated consent form. Document subject's informed consent in the subject's medical record.
- Screen the potential subject according to the study inclusion/exclusion criteria.
- Schedule the Baseline/Day 1 visit to occur after the results of the laboratory safety testing are received and any required washout period is completed.
- Record Demographic information including age, sex, race, ethnicity and Fitzpatrick skin type (Appendix B)
- Record medical history. Include information on subject's history of rosacea and any previous therapies, including:
 - The approximate date of physician's diagnosis of rosacea;
 - The subject reported signs and symptoms of rosacea,
 - How often they experience these symptoms?
 - Whether symptoms are continuous or occasional?
 - What, if anything, appears to trigger or worsen these symptoms?
 - Sunlight
 - Stress
 - Alcohol
 - Exercise
 - Hot and cold temperatures
 - Spicy food
 - Previous rosacea therapies within the previous 5 years;
- Review and record concomitant medications used in the last 30 days
- Assess whether the subject will require a washout period
- Perform a limited Physical Exam (refer to Section 7.5.2) with vital signs, height and weight measurements.
- Obtain a blood sample for hematology and chemistry analysis
- Perform an in-office urine pregnancy test on all females of childbearing potential.
- Perform the Investigators Global Assessment (IGA) of rosacea, the Investigators Assessment of Erythema (IAE) and Other Signs and Symptoms Assessment before performing the lesion count (refer to Section 7.4.1, 7.4.2, and 7.4.3). **It is important that the same evaluator performs the**

CONFIDENTIAL

Version Date: 31 March 2017

evaluations for the same subject at each visit, however it may not be feasible in all instances. Every effort should be made to maintain consistency of the evaluator for each subject.

- Perform the inflammatory lesion count (papules and pustules) (refer to Section 7.4.4). **It is important that the same evaluator performs the lesion count for the same subject, however it may not be feasible in all instances. Every effort should be made to maintain consistency of the evaluator for each subject.**

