7.2 SELECTION OF STUDY POPULATION

7.2.1 Inclusion Criteria

Subjects must meet each of the following criteria to be considered eligible for entry into the study:

1. Subjects who provided written informed consent to participate in the study.
2. Healthy, male and non-pregnant female subjects, 18 years of age or older.
3. A diagnosis of papulopustular rosacea with ≥ 30 inflammatory facial lesions (papules, pustules) at Baseline. Subjects must have no more than 2 nodular lesions, at Baseline.
4. Subjects with the presence of telangiectasia at Baseline.
5. Subjects with an erythema score of at least 2 on the Investigator Assessment of Erythema (IAE) scale at Baseline.
6. Subjects with a grade 4 (severe rosacea) on the 5-point Investigators Global Assessment (IGA) scale at Baseline.
7. Non-nursing, female subjects of child bearing potential, who are using a highly effective form of birth control or females not of childbearing potential due to menopause (must be postmenopausal for at least one year).
 - Highly effective methods of birth control are defined as those, alone or in combination, that result in a low failure rate (i.e. less than 1% per year) when used consistently and correctly. Forms of birth control include: Oral (birth control pills), Intravaginal: (e.g. NuvaRing®), Implantable (e.g. Norplant®), injectable (e.g. Depo-Provera®) or transdermal (e.g. Ortho Evra®) contraception; intrauterine device (IUD); double-barrier (diaphragm or condom with spermicidal gel or foam); for two months prior to study enrollment (see exclusion criteria #6) or a vasectomized partner or true abstinence (in line with preferred and usual lifestyle of subject) with an acceptable form of birth control should the subject become sexually active.

CONFIDENTIAL

Version Date: 31 March 2017

Periodic abstinence (e.g., calendar, ovulation, symptothermal, post-ovulation methods) and withdrawal are not acceptable methods of contraception. All female subjects of child bearing potential must undergo an in-office, highly sensitive urine pregnancy test, with a negative result, prior to being randomized to receive study drug. In addition, women of childbearing potential must agree to have a highly sensitive urine pregnancy test at the end of the study.

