7.4.4 Inflammatory Lesion Counts

The area of lesion count assessment is defined as the face from the jaw line to the hairline. The lesion counts will be performed at each study visit during the double-blind study period (Baseline, Week 1, 3, 6, 9, and 12) and at Week 26 and Week 52 during the open-label extension study period. The Investigator Global Assessment (IGA), Investigator Assessment of Erythema (IAE) and Other Signs and Symptoms Assessment should be performed prior to performing the lesion count at all visits, as indicated.

The lesion counts will be performed as follows:

Instructions On Performing Inflammatory Lesion Counts:

1. Subjects should have washed their face and removed all makeup at least 15 minutes prior. Male subjects should have already shaved before the study visit.
2. Subjects should be seated at arm's length (or slightly closer) from the evaluator performing the lesion counts and at the same height as the assessor. Subjects should not be seated in direct sunlight.
3. The room should have a balanced and consistent artificial or natural light source.
4. The **Principal Investigator or appropriately qualified Sub-Investigators** participating in this study will perform **all** lesion counts. It is essential that the same assessor perform all lesion counts for a given subject for the duration of that subject's participation in the study.
5. Lesions on each area of the face should be considered separately according to the diagram below. Lesions should be counted just to the hairline and no lower than the mandibular line (jaw

CONFIDENTIAL

Version Date: 31 March 2017

line). Scan each section of the face systematically from left to right and count only one lesion type at a time. Record each count on the source documents and initial your counts.

6. ALL LESIONS COUNTED SHOULD BE PALPABLE. If a lesion is not palpable it should be considered non-active (emerging or resolving). Post-inflammatory lesion pigment changes should not be counted. The inflammatory lesion count includes the total count of papules and pustules, which are defined as follows:

[figure not shown]
PAPULE – A type of inflammatory lesion; a small erythematous, palpable lesion, usually solid ≤ 0.5 cm in diameter.

PUSTULE – A type of inflammatory lesion; a small palpable lesion with an erythematous base approximately 0.5 cm in size and containing pus or yellow-white liquid.

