#### **5.4.3 Efficacy Analysis**

The co-primary endpoint of absolute change from baseline in inflammatory lesions will be analyzed using an Analysis of Covariance (ANCOVA) model, with treatment as a main effect, and baseline inflammatory lesions and pooled center as covariates. To investigate consistency of efficacy results across study centers, treatment by center interaction will be tested at 0.1 level of significance, and if significant, it will be further be explored.

The co-primary endpoint of IGA will be tested in the following manner: the 2 point reduction and the Clear or Almost Clear (0, 1) will be tested using the Hochberg procedure as follows: Statistical significance will be concluded if both endpoints are significant at a two-sided 0.05 level, or if either endpoint is significant at a two-sided 0.025. Both IGA endpoints will be analyzed using a Cochran–Mantel–Haenszel (CMH) test with center as the stratification factor. If the overall IGA response rates are less than 10%, a Fisher’s Exact test will be used to corroborate the CMH test. All tests of the co-primary endpoints will be analyzed.

If the co-primary endpoints of absolute lesion reduction and the two IGA endpoints (2 point reduction, and Clear or Almost Clear (0, 1)) are significant, the secondary endpoints will be tested sequentially in the order listed as follows:

- Test first secondary endpoint at 0.05. If not significant, stop; otherwise,
- Test second secondary endpoint at 0.05. If not significant, stop; otherwise,
- Test third secondary endpoint at 0.05 using Hochberg (similar to the primary method). If not both IGA (0,1) and IGA 2 point reduction are significant, stop; otherwise,
- Test fourth secondary endpoint at 0.05 using the Hochberg method.

For all efficacy analyses, small centers may be pooled in order to ensure sufficient cell counts for statistical testing.

Subgroup summaries (e.g. Gender, Age, Race, and Center) of the co-primary endpoints will be performed.

[figure not shown]

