#### 6.1 Baseline and Follow-Up Visits

Visits and time points (Double-blind period: baseline, interim [Weeks 1, 3, 6 and 9], final visit [Week 12]; Safety extension period: Weeks 16, 26, 39 and Week 52) for all analyses will be as record on the eCRFs , except as noted below. Baseline will be the later of the non-missing values from the Screening and Baseline/Day 1 visits scheduled to occur prior to receiving study medication. Unscheduled visits will not be used in any analyses but will be included on data listings.

If a subject does not complete the Double-Blind Study Period, the final double-blind visit (Week 12) will be reassigned to a scheduled visit based on the relative day ranges in the following table (where Day 1 is the first day of dosing). If a result already exists for the calculated visit or the calculated visit was not a scheduled visit, the next scheduled visit will be assigned.

Study Day Range	Calculated Visit
$2 \leq \text{Study Day} \leq 15$	Week 1
$16 \leq \text{Study Day} \leq 32$	Week 3
$33 \leq \text{Study Day} \leq 53$	Week 6
$54 \leq \text{Study Day} \leq 74$	Week 9
$\text{Study Day} \geq 75$	Week 12

If an Open-Label subject does not complete the study, the final open-label visit (Week 52) will be reassigned to a scheduled visit based on the relative day ranges in the following table. If a result already exists for the calculated visit or the calculated visit was not a scheduled visit, the next scheduled visit will be assigned.

Study Day Range	Calculated Visit
$89 \leq \text{Study Day} \leq 148$	Week 16
$149 \leq \text{Study Day} \leq 228$	Week 26
$229 \leq \text{Study Day} \leq 319$	Week 39
$\text{Study Day} \geq 320$	Week 52

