## 6.2 Missing Data

The primary method of dealing with missing data is multiple imputation (MI) technique. All co-primary and secondary endpoints will be analyzed using MI for missing data. As a sensitivity analysis, Observed Case and Baseline Observation Carried Forward (BOCF) will be utilized for the co-primary endpoints only.

The MI technique will be implemented as follows:

a) 100 imputed datasets will be generated to impute missing data using the below SAS code.

1) For inflammatory lesions

```
Proc MI NIMPUTE=100 SEED=20170531  
MIN = . 0 0 0 0 0 0  
MAX = . . . . . . .  
ROUND = . 1 1 1 1 1 1;  
class sex;  
var sex base w1 w3 w6 w9 w12;  
fcs reg(w1) reg(w3) reg(w6) reg(w9) reg(w12);  
run;
```

2) For IGA

```
Proc MI NIMPUTE=100 SEED=20170531  
MIN = . 0 0 0 0 0  
MAX = . 4 4 4 4 4  
ROUND = . 1 1 1 1 1;  
class sex;  
var sex w1 w3 w6 w9 w12;  
fcs reg(w1) reg(w3) reg(w6) reg(w9) reg(w12);  
run;
```

b) The 100 imputed datasets will each be analyzed separately by the methods described in Section 5.4.2.

1) For inflammatory lesions, individual LS means and associated standard errors as well as estimates and standard errors from the pairwise comparison of treatments from the analysis of each imputation will be combined into single estimates, standard errors, and p-value using PROC MIANALYZE as displayed below.

```
Proc MIANALYZE;  
Modeleffects estimate;  
Stderr stderr;  
run;
```

The p-value for the treatment by center interaction will be based on the average of p-values from each the analyses of each imputation.

- 2) For IGA, estimates of the event rates will be based on the average of rates from each imputation. The CMH test statistic from the analysis of each imputation will be converted to a Normal Z score by taking the square root and adjusting for direction (change to a negative value if Omiganan group is worse than Vehicle). These Z scores (with SE=1) will be combined into a single p-value using PROC MIANALYZE as displayed below:

```
Proc MIANALYZE;  
Model effects estimate;  
Stderr SE;  
run;
```

Similarly, the p-values for the one-sided Fisher's Exact test of each imputation will be converted to a Normal Z score using the inverse normal function. These Z scores (with SE=1) will be combined into a single p-value using the same PROC MIANALYZE code.

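### The Screening lesion count, taken before randomisation, is left out of the lesion ANCOVA and its imputation model; adding it could narrow the interval at almost no cost

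*Protocol*

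**What the plan says.** **Two counts before treatment.** The procedures table (protocol 7.3.1) marks inflammatory lesion counts at both Screening and Baseline. The visit instructions agree: at Screening the evaluator is to "Perform the inflammatory lesion count (papules and pustules) (refer to Section 7.4.4"), and the same step appears at Baseline, listed before randomisation and first application. Protocol 7.4.4 differs. It lists the counts at "each study visit during the double-blind study period (Baseline, Week 1, 3, 6, 9, and 12") and does not mention Screening.

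**Entry.** Inclusion criterion 3 requires "A diagnosis of papulopustular rosacea with ≥ 30 inflammatory facial lesions (papules, pustules) at Baseline".

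**Analysis.** SAP 6.1 states: "Baseline will be the later of the non-missing values from the Screening and Baseline/Day 1 visits". The lesion ANCOVA in SAP 5.4.3 is specified "with treatment as a main effect, and baseline inflammatory lesions and pooled center as covariates". The lesion imputation step in SAP 6.2 has the variable list "var sex base w1 w3 w6 w9 w12", with a single pre-treatment count. SAP 7.0 explains that the baseline covariate was added to the protocol's model because baseline counts vary widely.

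**The concern.** The sponsor has already accepted that pre-treatment lesion count should be adjusted for. One count of a fluctuating condition is a noisy measure of a subject's severity, and the protocol concedes that the evaluator may not always be the same. A second pre-randomisation count on the same subject may carry further information about the Week 12 count. If it does, adjusting for both removes more between-subject variation than adjusting for one.

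What is at stake is the precision of the lesion co-primary and of the Week 9 and Week 6 lesion endpoints, which come first in the secondary testing sequence. In the imputation step the Screening count could also add information for subjects who leave early with few post-baseline counts. Validity is not in question: the planned ANCOVA is sound as it stands.

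**Working it through.** **Inputs from the documents** (protocol 7.7.1 to 7.7.3, SAP 5.1): difference 13.5 − 4 = 9.5 lesions; SD of change 12; two-sided alpha 0.05; 1:1 allocation; 43 per group for 95% lesion power; 225 per arm set by IGA (17% versus 6%).

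**Inputs assumed:** all between-visit correlations. The documents give none.

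**1. Reproduce the plan.** With the noncentral t, 42 per group gives power 0.9479 and 43 gives 0.9524, so 43 per group is confirmed. For IGA, exact two-sided Fisher power at 225 per arm is 0.951, also confirmed. With 225 per arm, the lesion comparison at 9.5 and SD 12 has power above 0.9999.

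**2. Residual variance with one and two counts.** Let b be the Baseline–Week 12 correlation, s the Screening–Week 12 correlation, and c the Screening–Baseline correlation.
- One count: 1 − b².
- Two counts: 1 − R², with R² = (b² + s² − 2bsc)/(1 − c²).
- Variance ratio: (1 − R²)/(1 − b²). The standard error ratio is its square root.

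| b | s | c | Variance ratio | SE ratio | 450 subjects act as |
|---|---|---|---|---|---|
| 0.3 | 0.3 | 0.3 | 0.947 | 0.973 | 475 |
| 0.5 | 0.5 | 0.5 | 0.889 | 0.943 | 506 |
| 0.7 | 0.7 | 0.7 | 0.830 | 0.911 | 542 |
| 0.5 | 0.5 | 0.7 | 0.941 | 0.970 | 478 |
| 0.5 | 0.4 | 0.7 | 0.993 | 0.997 | 453 |
| 0.5 | 0.35 | 0.7 | 1.000 | 1.000 | 450 |
| 0.6 | 0.48 | 0.8 | 1.000 | 1.000 | 450 |

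The first four rows let both counts predict Week 12 equally well. The last two have s = b × c (0.5 × 0.7 = 0.35; 0.6 × 0.8 = 0.48): Screening then predicts Week 12 only through Baseline, and the gain is exactly zero.

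**3. Does the entry cut at 30 matter?** A simulation with assumed untruncated mean 35, SD 15 and common correlation 0.5, keeping only Baseline counts of 30 or more, lowers the Baseline–Week 12 correlation to 0.36 and leaves Screening–Week 12 at 0.42. The variance ratio stays at 0.889 (0.830 at correlation 0.7). The cut weakens the Baseline correlation but leaves the relative gain unchanged.

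**4. Effect on power if the true difference is small.** The SD of 12 is for change from baseline, before covariate adjustment. With equal variances at both visits, the residual SD of the planned ANCOVA is 12 × √((1 + r)/2), where r is the Baseline–Week 12 correlation.
- r = 0.4: residual SD 10.04, SE = 10.04 × √(2/225) = 0.947.
- r = 0.6: residual SD 10.73, SE = 10.73 × √(2/225) = 1.012.

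Take an illustrative difference of 3.7 lesions. By the normal approximation, power is Φ(3.7/0.947 − 1.96) = 97.4% and Φ(3.7/1.012 − 1.96) = 95.5%. An illustrative 6% to 9% variance cut multiplies the SE by √0.94 = 0.970 to √0.91 = 0.954. Power rises to between 98.1% and 98.4% at r = 0.4, and to between 96.5% and 96.9% at r = 0.6. The gain is about 0.7 to 1.4 percentage points.

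**The case against.** The strongest reply is that nothing here is wrong. One pre-treatment covariate plus pooled center is a standard, valid ANCOVA, and SAP 7.0 already improved on the protocol's model. That stands: the point is a refinement.

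A second reply is that the gain may be nil, and this also stands. Screening can be up to 30 days before Baseline, and subjects are told at Screening to stop any medication that needs washout. A count taken on prior therapy, or subject to serial decay, may add little once Baseline is known. A reader might infer from equal-correlation formulas that some gain is guaranteed; the documents do not support that.

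Third, no planned decision depends on it. The lesion endpoint is heavily powered, IGA sets the sample size, and the co-primary rule also needs IGA to succeed, which this change does not touch.

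Three stronger readings should also be resisted.
- A reader might infer that the Screening count is never used. SAP 6.1 uses it when the Baseline value is missing.
- A reader might infer that every subject will have two counts. They are scheduled, but 7.4.4 omits Screening, and completeness cannot be assumed.
- A reader might infer a benefit for the futility decision. SAP 5.4.4 carries the efficacy methods into the interim, but its conditional power text covers only proportions and the algorithm figure is not shown, so this cannot be verified.

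**Conclusion.** The concern holds as an optional gain in precision. A scheduled pre-randomisation measurement is left out of the lesion ANCOVA and imputation model except as a fallback, and no reason is given. Including it is unbiased.

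The size rests wholly on assumed correlations: a 0% to about 17% reduction in residual variance, or 0% to 9% in the standard error. The upper figure corresponds to a common correlation of 0.7 across the three visits and is not a mathematical limit. Planned power and N = 450 do not change. A reader might infer that the single-count model leaves the lesion endpoint underpowered or biased by the entry cut. Neither follows: power at the planned effect is above 99.9%, and the treatment groups are randomised after the cut is applied. The benefit is a narrower interval for the lesion co-primary and the Week 9 and Week 6 lesion endpoints, with a modest power gain if the true effect is far below 9.5 lesions.

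**What to change.** Before unblinding:

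- **SAP 5.4.3:** add the Screening inflammatory lesion count as a second continuous covariate in the lesion ANCOVA, for the co-primary and the secondary lesion endpoints. Keep change from Baseline/Day 1 as the endpoint. Record the change in SAP 7.0.
- **SAP 6.2:** add the Screening count to the VAR list of the lesion PROC MI step. MIN, MAX and ROUND are positional, with seven entries for seven variables, so extend each by one entry in the matching position; otherwise the limits shift to the wrong variables. Impute the Screening count where it is missing.
- **Observed Case and BOCF analyses:** fill a missing Screening count with a value that ignores treatment, such as the overall mean, so that no subject is dropped for lacking the covariate.
- **Protocol 7.4.4:** reconcile its list of lesion-count visits with the procedures table in 7.3.1.

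Where SAP 6.1 substitutes Screening for a missing Baseline count, the two covariates coincide for that subject; the SAP should say that this is accepted.

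The cost is one degree of freedom, one added imputation variable and a short SAP revision. No new data are collected. If the Screening count proves uninformative, the degree of freedom is all that is lost statistically.
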